5.6 DOSAGE AND ADMINISTRATION

Investigational product will be dispensed to the subjects under the supervision of the Investigator or his/her designee. Subjects should not crush, break, chew, or dissolve the capsules or tablets. Subjects should wash hands with soap and water after handling drug product.

Capsules or tablets should be taken with food.

5.6.1 *Immediate-release Capsules*

5.6.1.1 *Dose Titration Period (Study APD811-003 Placebo-treated Subjects)*

Subjects who were assigned to placebo treatment in Study APD811-003 will undergo a Dose Titration Period of up to 9 weeks. All subjects will be on active treatment (ralinepag) in the open-label study, APD811-007.

The dose titration scheme will be the same as conducted in Study APD811-003. Subsequent dose escalations will continue until the MTD is determined, with a possible maximum total daily dose of 600 mcg (300 mcg BID) if tolerated. Subjects will be observed for at least 4 hours after the initial dose of ralinepag, and at each subsequent dose escalation. AEs, BP, and heart rate will be monitored during the observation period. The observation period may be extended based on the judgment of the Investigator. If deemed necessary by the Investigator, the subject may be monitored as an inpatient for the initial dose and/or subsequent increases in dose. The medical monitor should be notified in any instance that prolonged observation and/or inpatient monitoring is anticipated or required.

If a dose is not tolerated, the study drug should be decreased to the previous dose level. If the initial dose of 10 mcg BID is not tolerated, dosing may be decreased to 10 mcg QD.

If the initial dose is tolerated (10 mcg BID), then the dose will be increased in the following fashion at subsequent visits: 20, 30, 40, 60, 80, 100, 200, and 300 mcg BID. The dose may be escalated to a possible maximum total daily dose of 600 mcg (300 mcg BID) if tolerated.

Subjects may become symptomatic during the course of dose escalation, and adjustment up and/or down may be required to find the optimal dose for any given subject. Over the 9-week Dose Titration Period, there are opportunities to change the dose. If a particular dose is not tolerated, treatment may be reduced to a previous dose as directed by the Investigator. The dose may be decreased for safety/tolerability reasons at any time, but may not be increased without assessment in the clinic.

Table 3 indicates the dosing regimen during the Dose Titration Period.

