6.12.4 Assessment of Adverse Event Severity

The severity of each AE will be assessed at onset by a nurse and/or physician. When recording the outcome of the AE, the maximum severity of the AE experienced will also be recorded. The severity of the AE will be graded according to the Common Terminology Criteria for Adverse Events v. 4.03²⁰ definitions listed below:

Grade 1: Mild; asymptomatic or mild symptoms; clinical or diagnostic observations only; intervention not indicated.

Grade 2: Moderate; minimal, local or noninvasive intervention indicated; limiting age-appropriate instrumental Activities of Daily Living (ADL)*.

Grade 3: Severe or medically significant but not immediately life-threatening; hospitalization or prolongation of hospitalization indicated; disabling; limiting self-care ADL**.

Grade 4: Life-threatening consequences; urgent intervention indicated.

Grade 5: Death related to AE.

* Instrumental ADL refer to preparing meals, shopping for groceries or clothes, using the telephone, managing money, etc.

** Self-care ADL refer to bathing, dressing and undressing, feeding self, using the toilet, taking medications, and not bedridden.

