9.2.1.2 Adverse Events

The AEs will be coded using the most current MedDRA and tabulated, including categorical information of interest, such as onset and resolution times, time of onset relative to dose, severity at onset, maximum severity, causal relationship to study drug, and action taken.

All AEs will be listed by subject and will be summarized and expressed in terms of maximum severity and relationship to study drug.

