11 SAFETY ANALYSES

11.1 ADVERSE EVENTS

AEs are captured from the time the Informed Consent Form is signed. AEs that are ongoing at the parent study Termination Visit are recorded as continuing AEs in the APD811-007 study. All AEs with an onset date on or after the first dose of ralinepag in the APD811-007 study or AEs ongoing from the parent study will be included in data listings and summaries.

The AEs will be coded using the Medical Dictionary for Regulatory Activities, and all summaries will utilize the Preferred Term (PT) and/or System Organ Class (SOC). All AEs and serious adverse events (SAEs) will be organized by treatment group in the parent study and listed by subject number, including onset date (day) and time, stop date (day) and time, verbatim term, corresponding PT and SOC, seriousness, severity, relationship to study drug, action taken with study drug, and outcome.

The overall summary of AEs includes the number of subjects with any AE, the number of subjects with any study drug-related AEs, the number of subjects with AEs leading to study drug withdrawal, the number of subjects with any SAEs, the number of subjects with any severe AEs, and the number of subjects with any study drug-related severe AEs.

The summaries of AEs by SOC and PT will be provided by treatment group in the parent study and overall. The summaries of AEs, SAEs, severe AEs, AEs related to ralinepag, SAEs related to ralinepag, and AEs leading to permanent discontinuation of ralinepag will include the number (percent) of subjects and number of events for each reported PT.

The summary of AEs adjusted for length of ralinepag exposure will include the number (percent) of subjects and number of events for each reported PT, as well as the number of events per patient-years of exposure.

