13 APPENDICES**13.1 LIST OF TABLES**

Table titles suggested here may be altered or edited as appropriate by the clinical data programmers while maintaining the original intent of the summary.

Table Number	Table Title
14.1.1	Summary of Subject Accountability
14.1.2	Summary of Ralinepag Exposure
14.1.3	Summary of Ralinepag Exposure in APD811-003 and APD811-007 Studies
14.1.4	Summary of Demographics
14.1.5	Summary of Baseline Characteristics
14.1.6	Summary of PAH History
14.1.7	Summary of Study Entry Criteria
14.1.8	Summary of Ralinepag Dosing
14.1.9.1	Summary of Concomitant Medications Ongoing from the Previous Study
14.1.9.2	Summary of Concomitant Medications Added in Study APD811-007
14.2.1.1	Summary and Analysis of Clinical Worsening
14.2.1.2	Summary of 6MWD (meters) by Visit
14.2.1.3	Summary of WHO Functional Class by Visit
14.2.1.4	Summary of Hemodynamics by Visit
14.2.1.5	Summary of BNP and NT-proBNP by Visit
14.3.1.1	Overall Summary of Adverse Events
14.3.1.2	Summary of Adverse Events by System Organ Class and Preferred Term
14.3.1.3	Summary of Adverse Events by Preferred Term
14.3.1.4	Summary of Serious Adverse Events by Preferred Term
14.3.1.5	Summary of Severe Adverse Events by Preferred Term
14.3.1.6	Summary of Serious Adverse Events Related to Ralinepag by Preferred Term
14.3.1.7	Summary of Adverse Events Related to Ralinepag by Preferred Term
14.3.1.8	Summary of Adverse Events Leading to Permanent Discontinuation of Study Drug by Preferred Term
14.3.1.9	Summary of Adverse Events Adjusted for Length of Ralinepag Exposure
14.3.2.1	Listing of Deaths
14.3.2.2	Summary of Deaths
14.3.2.3	Listing of Serious Adverse Events
14.3.4.1	Summary of Hematology Data
14.3.4.2	Summary of Hematology Shifts from Baseline
14.3.4.3	Summary of Clinical Chemistry Data
14.3.4.4	Summary of Clinical Chemistry Shifts from Baseline
14.3.4.5	Summary of Urinalysis Data
14.3.4.6	Summary of Coagulation Data

Table Number	Table Title
14.3.4.7	Summary of Vital Signs
14.3.4.8	Summary of Electrocardiogram Parameters

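### The SAP omits, without declaring it, the protocol's AE summaries by maximum severity and by action taken, and does not define 'severe'

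*SAP*

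**What the plan says.** **Protocol.** Section 6.12.4 grades AEs by CTCAE v4.03, Grades 1 to 5. The word severe labels one level only: "Grade 3: Severe or medically significant but not immediately life-threatening". Grade 4 is the life-threatening level and Grade 5 is death. Section 9.2.1.2 commits to this: "All AEs will be listed by subject and will be summarized and expressed in terms of maximum severity and relationship to study drug". That section and 8.2.1 also name maximum severity and action taken among the items to be tabulated. Section 6.12.7.1 gives seven drug-action categories for the CRF, including Dose Reduced and Dose Interrupted.

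For former placebo subjects titrating on the IR capsules, 5.6.1.1 says: "If a dose is not tolerated, the study drug should be decreased to the previous dose level". Section 3.1 permits dose reduction on either formulation whenever safety or tolerability calls for it. Tolerability is part of the primary objective (2.1), and 9.2.1 makes safety the primary analysis.

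**SAP.** The overall AE summary in 11.1 has six rows. Three are any AE, drug-related AEs and SAEs. One is "the number of subjects with AEs leading to study drug withdrawal". The other two are "the number of subjects with any severe AEs, and the number of subjects with any study drug-related severe AEs". The summaries by preferred term cover all AEs, SAEs, severe AEs, "AEs related to ralinepag, SAEs related to ralinepag, and AEs leading to permanent discontinuation of ralinepag", and there is an exposure-adjusted table. In the list of tables (13.1), the one AE table devoted to a drug action is 14.3.1.8, "Summary of Adverse Events Leading to Permanent Discontinuation of Study Drug by Preferred Term". Otherwise severity and action taken are items in the AE listing, which carries "seriousness, severity, relationship to study drug, action taken with study drug, and outcome". Section 12 lists seven changes from the protocol; none concerns AE summaries.

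**The concern.** Doses in this study are individually titrated to what each subject tolerates. Stopping the drug is only one response to an AE; the protocol also provides for lowering or interrupting the dose. A report built from the planned tables could give the number of subjects with severe AEs and the number who withdrew. It could not show how AEs divide across the five grades. Nor could it show how many subjects had the dose reduced or interrupted because of an AE. Those two summaries speak most directly to tolerability, and the protocol already promises the data for both in tabulated form.

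Two further problems follow. Because *severe* has no grade range in the SAP, a programmer could follow the text exactly and still leave out the two worst grades. And because SAP 12 is silent, a reader who relies on it would believe that the AE analysis is the one in the protocol.

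**Working it through.** No planned figure is at issue (SAP 6 states that there was no sample size calculation), so the check is mainly a comparison of the two documents.

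**Step 1: promised against planned.**

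| Item | Promised in protocol | SAP tables 14.3.1.1 to 14.3.1.9 | SAP listing | Declared in SAP 12 |
|---|---|---|---|---|
| Maximum severity, Grades 1 to 5 | 8.2.1, 9.2.1.2 | None; only *severe*, in two rows of 14.3.1.1 and in 14.3.1.5 | Severity | No |
| Action: Drug Withdrawn | 8.2.1, 9.2.1.2 | Row in 14.3.1.1, and 14.3.1.8 | Yes | Not needed |
| Action: Dose Reduced | 8.2.1, 9.2.1.2 | None | Yes | No |
| Action: Dose Interrupted | 8.2.1, 9.2.1.2 | None | Yes | No |

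So 0 of 9 AE tables show the grade distribution, and 1 of the 7 drug actions is tabulated against AEs.

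**Step 2: can the dose table stand in?** SAP 9.3.5 and Table 14.1.8 summarise dose by visit and the number of subjects per dose category. Titration action is only listed. The table does not tie a dose change to an AE, and increases and decreases at the same visit offset each other. The move from IR to XR (Table 5 in Protocol 5.6.2.1) also changes the nominal total daily dose with no AE involved:

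- 80 to 50 mcg: (50 − 80)/80 = −37.5%
- 120 to 100 mcg: (100 − 120)/120 = −16.7%
- 160 to 150 mcg: (150 − 160)/160 = −6.25%
- 40 to 50 mcg: (50 − 40)/40 = +25.0%

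A shift in Table 14.1.8 therefore cannot be read as intolerance. (This takes no view on the conversion itself.) Only the action-taken field connects a reduction to an event.

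**Step 3: what a literal reading of *severe* does.** The planned size is about 60 (Protocol synopsis). The SAP row counts subjects with any severe AE. If severe means Grade 3 only, a subject with both a Grade 3 and a Grade 4 event is still counted. The subjects who drop out are those with at least one Grade 4 or 5 event and no Grade 3 event. Call their number k:

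shortfall = k/60, so k = 0 gives 0; k = 1 gives 1/60 = 1.7 points; k = 2 gives 2/60 = 3.3 points; k = 3 gives 3/60 = 5.0 points.

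Neither document gives k, so these values are arithmetic and not estimates. The tables are also split by parent-study group. Each group is smaller than the total, so one subject moves a group percentage by more than 1.7 points. The group sizes are not stated. In Table 14.3.1.5 the same rule applies within each preferred term, and each Grade 4 or 5 event also leaves the event count.

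**The case against.** The strongest reply is that the SAP tabulates a great deal more than severe AEs and withdrawals. It plans tables of all AEs, related AEs, SAEs, related SAEs and exposure-adjusted AEs, plus deaths (11.2), reasons for discontinuation (9.1) and dose by visit (9.3.5). The primary outcome measures in the protocol synopsis are treatment-emergent AEs and SAEs, and both have tables. Grade and dose action are listed for every event, in a study of about 60 subjects. Most readers would take severe to mean Grade 3 or higher. The step-down rule quoted above covers former placebo subjects in IR titration, where stepping down is also how the maximum tolerated dose is found. Section 9.2.1.2 prescribes no particular table layout.

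All of this is correct, and it rules out several stronger inferences that a reader might draw:

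- *Tolerability is measured only by severe AEs and discontinuations.* It is not, given the tables just named.
- *Most intolerance goes untabulated.* The documents give no rate of reduction, interruption or withdrawal. An AE that led to a reduction is still counted in the all-AE table. Protocol 1.1.3 does report mostly moderate AEs in a titration study, but in healthy volunteers, and 1.1.1 cautions that PAH may bring different responses.
- *Grade 4 and 5 events vanish.* Death and life-threatening events are SAE criteria (Protocol 6.12.2), so they should appear in the SAE tables, and deaths have their own summary. The risk is misclassification within one category.
- *Every subject whose worst event is Grade 4 or 5 leaves the severe count.* This is true only without a Grade 3 event as well.

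The reply does not cover the promised summaries. A listing is not a tabulation, the dose table cannot link a change to an event, and SAP 12 gives neither notice nor reason.

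**Conclusion.** The point holds in this form. The SAP departs from Protocol 8.2.1 and 9.2.1.2 by leaving out the maximum-severity summary and every drug action except withdrawal, and it does not declare the departure. The loss is one of presentation: the grade distribution, and the link between AEs and dose reduction or interruption. It matters because tolerability belongs to the primary objective and dose reduction is part of the protocol's answer to intolerance.

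The undefined *severe* is a smaller, related defect. Its effect is 1.7 percentage points overall for each subject with a Grade 4 or 5 event and no Grade 3 event. That figure assumes about 60 treated subjects and a Grade 3-only reading. The SAP neither states nor excludes that reading, and the number of such subjects may be zero. How many subjects had an AE-driven reduction or interruption cannot be told from the documents. The change should be made, but no planned result is invalid without it.

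**What to change.** In SAP 11.1:

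1. Define severe as CTCAE Grade 3 or higher, and apply that to both severe rows of Table 14.3.1.1 and to Table 14.3.1.5.
2. Add a summary of AEs by maximum grade, 1 to 5, by parent-study group and overall.
3. Add to the overall summary the number of subjects with AEs leading to dose reduction and the number with AEs leading to dose interruption. Versions by preferred term are optional, since the protocol does not fix the layout.

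If the sponsor decides against items 2 and 3, SAP 12 should list the omission and the reason for it.

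The cost is a few lines of SAP text and a few extra tables. Severity and action taken are already collected under Protocol 6.12.4 and 6.12.7.1, so no new data are needed. The sponsor should expect that the severity and tolerability figures may look less favourable than under the present plan.

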3 INVESTIGATIONAL PLAN

3.1 OVERALL STUDY DESIGN AND PLAN

This is a Phase 2, multicenter, open-label, extension study to determine the long-term safety and tolerability of ralinepag in subjects with WHO Group 1 PAH who have completed the Phase 2 study, APD811-003, or who were assigned to placebo and were discontinued for clinical worsening. Subjects must also meet eligibility criteria for participation in this long-term extension study. The Day 1 (Baseline) visit in Study APD811-007 will coincide with the Week 25 Visit in Study APD811-003. For this reason, subjects should be consented to Study

APD811-007 prior to the Week 25 procedures being performed for Study APD811-003. Baseline/Day 1 evaluations will include medical history update, assessment of disease state, and determination of eligibility for each potential subject.

All subjects enrolled in Study APD811-007 will receive open-label treatment with ralinepag. The starting dose and titration schedule will be individually determined in accordance with the starting dose and titration schedule optimized from Study APD811-003. Adjustments in the dose and titration schedule may be made according to subject tolerability. After the completion of Study APD811-003, ongoing safety review of subject data will be conducted by the Sponsor to monitor for drug safety.

After an individual subject completes Study APD811-003 and that subject's database is locked, subject unblinding will occur. Subjects who were on active treatment (ralinepag) in Study APD811-003 will remain on current dose and have onsite clinical assessments performed every 3 months until the subject is discontinued from the study (see Table 1).

Subjects in the placebo treatment group of Study APD811-003 will undergo a Dose Titration Period until a stable maximum tolerated dose (MTD) is reached (up to 9 weeks); this will be followed by a Treatment Period in which monthly onsite clinic assessments will be performed for the first 3 months and then every 3 months until the subject is discontinued from the study or the study is terminated (see Table 2).

Subjects will continue to have visits to the clinic every 3 months indefinitely to collect data as specified in Table 1 and Table 2 until marketing approval of ralinepag is granted or until the Sponsor discontinues the study.

During the conduct of the study, subjects will switch from the IR formulation of ralinepag (as studied in ADP811-003) to an XR formulation that will be used in Phase 3 studies.

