5.6.1.2 Treatment Period

Subjects who were on active treatment (ralinepag) in Study APD811-003 will remain on current dose and have onsite clinical assessments performed every 3 months until the subject is discontinued from the study (see Table 1). Subjects in the placebo treatment group of Study APD811-003 will undergo a Dose Titration Period until a stable MTD is reached (up to 9 weeks). At the conclusion of the Dose Titration Period and when a subject reaches the highest dose tolerated, the subject will transition directly into the Treatment Period with monthly assessments for the first 3 months and then every 3 months.

The optimal dose achieved for each subject at the end of the Dose Titration Period can be maintained throughout the Treatment Period; however, incremental dose increases will also be allowed during the Treatment Period at the discretion of the Investigator (as clinically indicated) and according to the stepwise titration scheme outlined in Table 4.

Table 4 indicates the possible IR dosing regimens to be used during the remainder of the Treatment Period according to each individual subject's optimally defined dose.

Table 4 Possible Dosing Regimen during the Treatment Period

Dose (mcg)		Supplied by		Total daily dose (mcg)
10	QD	1 × 0.01 mcg	QD	10
10	BID	1 × 0.01 mcg	BID	20
20	BID	1 × 0.02 mcg	BID	40
30	BID	1 × 0.03 mcg	BID	60
40	BID	1 × 0.04 mcg	BID	80
60	BID	2 × 0.03 mcg	BID	120
80	BID	2 × 0.04 mcg	BID	160
100	BID	1 × 0.1 mcg	BID	200
200	BID	2 × 0.1 mcg	BID	400
300	BID	3 × 0.1 mcg	BID	600

Abbreviations: BID, twice daily; QD, once daily

5.6.2 *Extended-release Tablets***5.6.2.1** *Formulation Switch and Dose Titration Period*

During the study, all subjects will switch to an XR formulation of ralinepag that will be used in Phase 3 studies of ralinepag, per the guidance in Table 5. The switch to XR ralinepag should occur at a regularly scheduled visit, with dose titration to occur, as needed, in 50-mcg weekly increments. Weekly phone contact with the subject will be performed to guide XR dose titration to the highest tolerated dose.

Table 5 Dose Switching Guidance from Immediate-release to Extended-release Ralinepag

Current IR Dose (mcg; total daily)	Corresponding XR Dose (mcg)
<30	50 EOD
≥30 to <120	50
120	100
160	150
200	200
400	400
600	600

Abbreviations: EOD, every other day; IR, immediate-release; XR, extended-release

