6.12.1 Adverse Event Reporting

Subjects will be instructed that they may report AEs at any time. All events reported following study drug administration will be recorded as TEAEs.

Monitoring of AEs will be continued up to 30 days after cessation of study drug administration. In the event that an AE is not resolved or stabilized by this time, the Sponsor in consultation with the Investigator will decide whether to continue to monitor the AE or close-out the event in the database if no further follow-up is necessary.

For this study, an AE is defined as: “Any untoward medical occurrence in a study subject administered any dose of ralinepag and which does not necessarily have to have a causal relationship with this treatment.” An AE can therefore be any unfavorable and unintended sign (including an abnormal laboratory finding), symptom, or disease temporally associated with the use of the study drug, whether or not related to the product.

AEs can be any of the following:

- Unfavorable changes in general condition
- Subjective or objective signs/symptoms
- Concomitant disease or accidents
- Clinically relevant adverse changes in laboratory parameters observed in a subject in the course of a clinical study
- Pre-existing conditions which worsen in severity or frequency or which have new signs/symptoms associated with them

AEs will be elicited at the time indicated in the schedule by asking the question, “Since you were last asked, have you felt unwell or different from usual in any way?” Any adverse or unexpected events, signs, and symptoms will be fully recorded on the AE Form, including details of intensity, onset, duration, outcome, and relationship to the drug as determined by

the Investigator. Whenever possible, a constellation of signs and symptoms should be recorded as a unifying diagnosis (eg, self-limited fever, runny nose, cough, and scratchy throat should be captured as an upper respiratory infection rather than by the individual signs and symptoms). AEs may also be reported at any time. The type and duration of follow-up of subjects after AEs will be documented.

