7.2 STUDY PROCEDURES

7.2.1 *Baseline Study Procedures – All Subjects*

Subjects who meet all the entry criteria and are eligible for the study will report to the clinical study unit to confirm eligibility for the study and complete all Baseline procedures and receive study drug and instructions. The study drug will be given in the morning at the study site during the Baseline Visit.

7.2.1.1 *Pre-baseline Procedures*

All Week 25 measurements from Study APD811-003 will serve as Baseline assessments for Study APD811-007.

Placebo-treated subjects who discontinued prematurely from Study APD811-003 due to clinical worsening are permitted to enroll in APD811-007 provided that all end of study procedures are performed per the ADP811-003 protocol. For these subjects, the time of the clinical worsening event that led to early termination in Study APD811-003 will serve as the Baseline time point for clinical worsening in APD811-007.

Any unresolved AE from Study APD811-003 will be carried forward and recorded.

7.2.1.2 *Baseline Procedures*

- Medical history (partial history, to update findings from Study APD811-003)
- Physical exam¹
- 12-lead ECG¹
- Clinical laboratory tests (to include hematology, coagulation parameters, serum chemistry, and urinalysis)¹
- Serum pregnancy test (women only)¹
- Vital signs¹
- 6MWT¹
- BNP/NT-proBNP¹
- Assessment of clinical worsening

- WHO/NYHA FC assessment¹
- Record AEs¹
- Record concomitant medications¹

¹ Taken from Week 25 Visit in Study APD811-003

7.2.2 Study Procedures – for Immediate-release Dose Titration Period (Study APD811-003 Placebo Subjects)

Visits after Baseline should occur weekly for each escalation of study drug dose. There should be 1 study visit per week during the Dose Titration Period. Beyond the weekly visit, any additional visit during the Dose Titration Period will be documented as an ‘unscheduled’ visit.

If a subject reaches a stable MTD and no further dose escalations are planned, the Dose Titration Period will be considered completed and will be followed by monthly assessments for the first 3 months and then every 3 months until the subject is discontinued from the study, Sponsor termination of the study, or the last subject enrolled completes approximately 6 months of treatment with ralinepag.

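### By-arm AE tables pool an early period in which the two parent arms are questioned and tested at very different frequencies, so part of any early difference may be detection

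*SAP*

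**What the plan says.** **Display.** SAP 11.1: "The summaries of AEs by SOC and PT will be provided by treatment group in the parent study and overall". It adds one exposure-adjusted table (14.3.1.9, events per patient-years). No AE table in SAP 13.1 is split by study period.

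**How AEs are found.** Protocol 6.12.1: "AEs will be elicited at the time indicated in the schedule by asking the question"; the question covers the time since the previous enquiry. The same section adds: "Subjects will be instructed that they may report AEs at any time". Its definition of an AE includes abnormal laboratory findings.

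**Ex-placebo schedule.** Protocol 5.6.1.1: "Subjects who were assigned to placebo treatment in Study APD811-003 will undergo a Dose Titration Period of up to 9 weeks". Protocol 7.2.2: "There should be 1 study visit per week during the Dose Titration Period". Titration may end sooner: "If a subject reaches a stable MTD and no further dose escalations are planned, the Dose Titration Period will be considered completed". After that, under Protocol 3.1, "monthly onsite clinic assessments will be performed for the first 3 months and then every 3 months until the subject is discontinued from the study". Table 2 marks AE monitoring at every one of these visits.

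**Ex-ralinepag schedule.** Protocol 5.6.1.2 says these subjects "will remain on current dose and have onsite clinical assessments performed every 3 months". Table 1 marks AE monitoring at Baseline and then only at the 3-monthly visits until End of Study and follow-up.

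**Onset timing.** Protocol 8.2.1 and 9.2.1.2 plan to tabulate AE onset relative to dose. SAP 11.1 carries onset date and day in the listing only, and SAP 12 does not declare the missing tabulation as a change.

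**The concern.** Safety is the primary analysis (Protocol 9.2.1), and its main tables put the two parent arms side by side. In the early months the arms differ in how often AEs are looked for, quite apart from how often they occur. Two mechanisms are at work:

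- **Questioning.** The recall interval is about 1 to 4 weeks in one arm and about 13 weeks in the other. Protocol 1.1.3 lists headache, nausea, diarrhea, jaw pain and flushing as the commonest AEs in the parent study. These are symptoms, and reporting them may depend on the recall interval.
- **Testing.** Events visible only on an ECG, a laboratory test or post-dose blood pressure can be found only when the test is done. This needs no assumption about memory.

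At stake is how the columns are read. Protocol 3.2 remarks that tolerability may improve with continued exposure. A lower ex-ralinepag column could be taken as support for that, when some of the gap may come from the visit schedule.

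**Working it through.** The plan gives no figure to reproduce, so the check is a count of scheduled post-baseline visits with AE monitoring.

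**Inputs.** Titration of T weeks, T = 1 to 9, with one visit a week (Protocol 5.6.1.1, 7.2.2). Then M1, M2, M3, then every 3 months (3.1, Table 2). Ex-ralinepag: every 3 months from entry (3.1, 5.6.1.2, Table 1). Window ±5 days for 3-monthly visits, ±3 days otherwise (6.15). One month = 365.25/12/7 = 4.35 weeks, so 3 months = 13.04 weeks.

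**1. Early window.** 9 + 13.04 = 22.0 weeks.
- Ex-placebo enquiries: T + 3, which is 4 (T = 1) to 12 (T = 9).
- Ex-ralinepag enquiries: 1, at about Week 13. Month 6 falls at Week 26.1, and at the earliest at 26.1 − 5/7 = Week 25.4.
- The Baseline visit is common to both arms and is not counted.

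**2. Testing in the same window, with T = 9.**
- Laboratory occasions: 3 (Weeks 2, 5, 9) + 3 (M1 to M3) = 6 against 1.
- ECG visits: 9 + 3 = 12 against 1. Titration visits have a pre-dose and a 2-hour post-dose recording; in Table 1 the ECG is pre-dose only.
- Vital signs hourly for 4 hours after dosing: ex-placebo titration visits only (7.2.2.2, Table 2).

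**3. Over the whole study, with T = 9 and XR-switch calls excluded.**

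| Time | Ex-placebo | Ex-ralinepag | Ratio |
|---|---|---|---|
| 6 months | 12 | 2 | 6.0 |
| 1 year | 14 | 4 | 3.5 |
| 2 years | 18 | 8 | 2.25 |
| 4 years | 26 | 16 | 1.6 |

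The excess stays at 10 enquiries while the ratio shrinks. The problem is confined to the early period.

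**4. Possible size, by assumption only.** Suppose the chance that an event is still reported at the next enquiry halves every h weeks. Average capture over an interval of L weeks is c(L) = (1 − e^(−λL))/(λL), with λ = ln 2/h. With equal true rates, the ratio over 22 weeks is [9·c(1) + 13·c(4.35)]/22 divided by c(13.04).

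| h (weeks) | Ex-placebo capture | Ex-ralinepag capture | Ratio |
|---|---|---|---|
| 4 | 0.791 | 0.396 | 2.0 |
| 13 | 0.926 | 0.721 | 1.28 |
| 26 | 0.962 | 0.845 | 1.14 |
| 52 | 0.980 | 0.918 | 1.07 |
| perfect recall | 1 | 1 | 1.00 |

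No value of h is given in the documents. The table covers questioning only, not testing.

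**5. Where to cut.** The ex-placebo Month 3 visit falls between Week 1 + 13.04 = 14.0 and Week 22.0, or Week 22.5 with the 3-day window. A cut at each subject's own Month 3 would therefore vary with titration length. A cut at Week 22 would fall between the ex-ralinepag visits at Weeks 13 and 26. Week 26 (26 × 7 = Day 182) lies after the latest ex-placebo Month 3 visit and coincides with the ex-ralinepag Month 6 visit. From then on both arms are on the 3-monthly schedule.

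**The case against.** The case against has real weight.

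- **Spontaneous reporting is open.** Subjects may report AEs at any time, and the visit question covers the whole interval, so quarterly questioning leaves no gap in coverage. AEs ongoing from the parent study are also carried into the summaries (SAP 11.1). This stands: the questioning effect may be small or nil. It does not touch events seen only on a test.
- **A true early difference is expected.** Ex-placebo subjects are titrated on first exposure. Ex-ralinepag subjects continue an established dose, and those withdrawn for AEs were excluded (Protocol 4.3). This stands: titration and close contact coincide, and no tabulation of the early period can separate them. That is a reason to show the period apart from the rest.
- **The tables are descriptive.** There is an overall column, no between-arm AE test is planned, and neither document says the columns will be read as tolerance developing. This stands, and it limits the point to one of interpretation.
- **The later period is not purely quarterly.** Weekly calls accompany the XR switch (Protocol 5.6.2.1, 7.2.3.3). These apply to both arms, so they create no systematic difference in the schedule.

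A reader might go further and infer that part of the arm difference *is* detection, or attach a definite ratio to it. The documents do not support that. They show neither an arm difference nor under-recall, and they give no capture rate. Nor do they describe the commonest AEs as mild; Protocol 1.1.3 reports that in the Phase 1 multiple-dose study most AEs on active drug were moderate.

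**Conclusion.** The point holds as a limited one. Ascertainment is unequal by design in about the first 22 weeks: up to 12 enquiries against 1, 6 laboratory occasions against 1, and 12 ECG visits against 1. The SAP pools that period with later follow-up in by-arm tables. Dividing by patient-years does not remove the imbalance. Part of any early difference may be detection. How much cannot be derived; the assumed range of 1.00 to 2.0 includes no effect, and the influence on whole-study tables is diluted as follow-up lengthens.

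The counts rest on ex-ralinepag subjects following Table 1, as Protocol 3.1, 5.6.1.2 and 5.7 describe. Protocol 3.2 instead speaks of re-titrating every entrant. Those passages must be reconciled. The figure of 12 is the maximum, reached only with a full 9-week titration.

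This is a worthwhile, inexpensive improvement to a descriptive display. It is not a flaw that invalidates the safety analysis.

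**What to change.** 1. For AE tables not confined to serious events or discontinuations (14.3.1.2, 14.3.1.3, 14.3.1.5, 14.3.1.7) and for the exposure-adjusted table (14.3.1.9), add a split by AE onset at one fixed study day in both arms, for example Week 26 (Day 182 from first APD811-007 dose).
2. Count patient-years within each period, and use subjects still under observation at the cut as the later denominator. Show AEs ongoing from the parent study on a separate row, since their onset precedes both periods.
3. Leave the SAE tables (14.3.1.4, 14.3.1.6) and the discontinuation table (14.3.1.8) unsplit.
4. State in SAP 11.1 that contact and testing schedules differ before the cut, that the early period cannot separate detection from titration, and that any cross-arm statement rests on the later period, SAEs and discontinuations. Note that XR-switch calls apply to both arms.
5. Record in SAP 12 what became of the protocol's tabulation of onset relative to dose. The split restores part of it.
6. Reconcile Protocol 3.2 with 3.1, 5.6.1.2 and 5.7.

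**Cost.** SAP wording, one derived period variable from onset dates already listed, and a few more tables with smaller counts per cell. No new data are needed. For ex-placebo subjects the cut falls between visits, so some events near it are still placed by recalled onset date. The later period removes the schedule difference but not the selection of completers.
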